
STATISTICAL DESIGN AND POWER

Sample Size and Power

The total proposed enrollment of 280 women was determined considering a feasible rate of recruitment, expected effect size of the AME intervention on primary outcomes, testing of multiple hypotheses, and anticipated rate of attrition and protocol non-adherence at 2 weeks postpartum (primary outcome assessment). Our recent intervention research with normal weight and overweight/obese women demonstrates medium sized effects (standardized mean difference, d) for the AME intervention at 1-2 weeks postpartum compared to an education control in terms of higher levels of breastfeeding selfefficacy (AME: M=52.59, SD=9.92, Education: M=45.71, SD=15.71, d=0.53) and greater percentage of breast milk feeds (AME: M=89.50, SD=20.372; Education M=78.64, SD=27.303, d=0.45). Regarding exclusive breastfeeding at 1-2 weeks, rates of 0.27 have been reported among overweight/obese women.32 With a sample size of at least 210 (105 per group), we can detect with .80 power betweengroup differences in the proportions in breastfeeding exclusivity at 2 weeks postpartum as small as .172 (medium effect size of OR=2.55 using likelihood ratio chi-square statistics) at an adjusted test-wise significance level of .0167. While there is a fair amount of heterogeneity in the published effect sizes for breastfeeding support interventions among overweight and obese women and for AME specifically, our estimate lies in the range of reported effect sizes in the field. 12,32 While the examination of long-term efficacy of AME is more exploratory (Aim 2), we will be able to detect small to medium interaction effects between groups over time as small as f = .323 when using repeated measures F-tests with at least four postpartum outcome time points. Our pilot work and previous studies utilizing similar populations and recruitment sites indicate that we can conservatively anticipate combined study attrition and intervention dropout at ≈25%. To ensure 210 participants with complete follow-up to 2 weeks and no protocol deviations, we will enroll 280 women.

Statistical Methods

Preliminary Analyses: For Aims 1 and 2, detailed exploratory data analyses will first be performed, involving data description and data screening for anomalies (e.g., outliers, nonnormality, etc.). The results from this initial investigation will be used to: 1) describe

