univariate and bivariate data distributions; 2) identify imbalances between treatment groups and associations between the dependent variables and suspected covariates/confounders; 3) evaluate the amount and patterns of missing data; and 4) check for violations of statistical assumptions for the planned analyses. If statistical assumptions are seriously violated, data transformations or more statistically robust methods will be considered. Covariates/confounders will be included in models secondarily, and their impact on the effect of the primary independent variable on the study outcomes will be evaluated. The randomness of missing data will be investigated using available information on subject characteristics to help discern patterns in the missing data, identify the possible covert missing data mechanisms, and inform the choice of the strategies to handle missing data. We will conduct logistic regression models to compare the characteristics of participants who remained in the study versus those who dropped out to determine if data are missing at random. If data are ignorably missing (i.e., not related to the outcome itself), likelihood estimation procedures, such as those in SAS PROC MIXED, GLIMMIX and NLMIXED as well as Mplus, will produce unbiased estimates while allowing us to retain cases with missing values on the outcome variables. If needed, multiple imputation would be used to impute missing values on the predictor variables. If data are not ignorably missing (i.e., non-randomly missing), we may use pattern mixture modeling to account for informative attrition.

Analysis Strategies for Aims 1 and 2: To examine the efficacy of the remotely-delivered AME intervention relative to the attention control on breastfeeding outcomes during hospitalization to the first two weeks postpartum (short-term; Aim 1) and up to the first 12 months (long-term; Aim 2) among overweight and obese (BMI \geq 25) women, an intent-to-treat (ITT) approach will be used, where all participants will be included in analyses as randomized, regardless of protocol adherence/deviations, treatment received, or withdrawal. Adherence to the assigned intervention, however, will be monitored, and the sensitivity of the results under the ITT model will be explored to identify the effects of the amount of intervention received (e.g., number of AME study visits) and deviations in protocol on outcomes.

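### The .172 difference in 2-week exclusive breastfeeding does not have 80% power as a gain from 27%: power is about 59%, and the gain detectable at 80% is .215

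*Combined protocol and SAP*

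**What the plan says.** All the figures stand in one paragraph of Sample Size and Power, under Statistical Design and Power.

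- Reference rate: "Regarding exclusive breastfeeding at 1-2 weeks, rates of 0.27 have been reported among overweight/obese women". No other exclusivity rate is given, and neither arm's expected rate is named.
- Size and alpha: "With a sample size of at least 210 (105 per group"), tested "at an adjusted test-wise significance level of .0167".
- Detectable effect: "we can detect with .80 power betweengroup differences in the proportions in breastfeeding exclusivity at 2 weeks postpartum as small as .172", with the parenthesis "medium effect size of OR=2.55 using likelihood ratio chi-square statistics".
- Enrolment: "To ensure 210 participants with complete follow-up to 2 weeks and no protocol deviations, we will enroll 280 women". The allowance of about 25% combines study attrition with dropout from the intervention.

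Analysis Strategies for Aims 1 and 2 lists the proportion of mothers giving only breast milk at 2 weeks as the first of three primary outcomes. It says the contrasts look for greater improvement under AME. It sets an intent-to-treat analysis in which "all participants will be included in analyses as randomized, regardless of protocol adherence/deviations, treatment received, or withdrawal".

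**The concern.** A risk difference and an odds ratio given for the same detectable effect must agree once one of the two rates is fixed. Here they do not. This sentence is the only power statement for the first primary outcome, and the risk difference is the figure most readers will take from it. They will conclude that the trial would reliably detect a 17-point gain. If the result is null, that gain may be treated as excluded when the trial had about a 41% chance of missing it.

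A second, smaller question is whether the stated power belongs to the planned analysis at all. It is computed for women with complete follow-up and no deviations, whereas the analysis keeps everyone as randomized.

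**Working it through.** **Inputs from the plan:** reference rate p0 = .27; n = 105 per group, 1:1; alpha = .0167 (.05/3); target power .80; stated difference .172; stated OR 2.55; likelihood-ratio (LR) chi-square test; 25% allowance.

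**Assumptions:** .27 is the control-arm rate, and the test is two-sided, as a 1-df chi-square is. The plan states neither.

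**Step 1. Do the two effect sizes agree?**

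OR = [p1/(1−p1)] / [p0/(1−p0)], with p0/(1−p0) = .27/.73 = .3699.

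- Gain of .172: p1 = .442; .442/.558 = .7921; OR = .7921/.3699 = 2.14.
- OR 2.55: odds = 2.55 × .3699 = .9432; p1 = .9432/1.9432 = .485; difference = .215.
- Fall of .172: p1 = .098; .098/.902 = .1086; OR = .3699/.1086 = 3.40 (inverted).

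They do not agree. The only pairs of rates with both a difference of .172 and an OR of 2.55 are about .168 vs .340 and its mirror image, .660 vs .832. Neither contains .27, and power there is only about .69.

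**Step 2. Reproduce the plan's figures.**

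Pooled z: power = Φ[(|p1−p0| − z·s0)/s1], where

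- z = 2.393 for two-sided .0167
- s0 = √[2p̄(1−p̄)/n], with p̄ the mean of the two rates
- s1 = √[(p0(1−p0) + p1(1−p1))/n]

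LR: the noncentrality is λ = 2n·Σ[p·ln(p/p̄) + (1−p)·ln((1−p)/(1−p̄))], summed over the two arms. It is referred to a 1-df noncentral chi-square with critical value 5.728.

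| Comparison | s0 | s1 | Pooled power | λ | LR power |
|---|---|---|---|---|---|
| .27 to .485 (OR 2.55) | .0669 | .0652 | .80 | 10.5 | .80 |
| .27 to .098 (−.172) | .0535 | .0521 | .801 | 10.69 | .809 |
| .27 to .442 (+.172) | .0661 | .0650 | .584 | 6.83 | .587 |

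For the last row: (.172 − 2.393 × .0661)/.0650 = .213, and Φ(.213) = .584.

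Solving for the effect with .80 power at 105 per group:

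- Increase: .215 (OR 2.55) by both methods.
- Decrease: .172 by pooled z, .171 by LR.

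So OR 2.55 reproduces as the detectable benefit, and .172 reproduces only as the detectable decrease.

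**Step 3. Does another method rescue a gain of .172?** No. At 105 per group and alpha .0167, power is .600 unpooled, .590 arcsine, .594 exact LR, .592 exact Pearson, .527 with continuity correction and .686 one-sided pooled. With all 280 women evaluable (140 per group) it is .73. Reaching .80 needs 161 per group, which is 322 evaluable, or 322/.75 ≈ 430 enrolled.

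**Step 4. Intent-to-treat dilution.** Split the 25% into loss to follow-up L and intervention dropout D, with L + D = .25. As an illustration, give dropouts control-level outcomes. Then n = 140(1−L) per group, and the true .215 becomes .215 × [1 − D/(1−L)].

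| L | D | n per group | Diluted difference | Power |
|---|---|---|---|---|
| .25 | 0 | 105 | .215 | .80 |
| .125 | .125 | 122.5 | .184 | .73 |
| 0 | .25 | 140 | .161 | .67 |

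**The case against.** The strongest reply is that the sample size is not shown to be wrong. The OR of 2.55 in the same sentence is a correct detectable benefit, and 210 evaluable and 280 enrolled are consistent with it. Only the risk difference is off. What a null result excludes will be read from the confidence interval, which the plan promises for every comparison. All of this stands. It limits the damage to a misstated figure, but it does not make that figure right.

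Three further points deserve an answer.

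- **Origin of .172.** That it came from the downward solution is an inference. The plan gives no direction, and the LR test it names gives .171 rather than .172. The gap of .001 is immaterial, and the error does not depend on how it arose.
- **Unstated inputs.** The plan does not call .27 the control rate or state sidedness. If .27 were the AME rate against a control rate of 9.8%, .172 would have .80 power, but the OR would be 3.40. If .27 were the average of the two arms, power would be about .66 and the OR 2.45. A one-sided test gives .69. No reading makes the sentence consistent.
- **Intended target.** The plan does not say whether .172 or OR 2.55 was the aim. But the sentence states what 105 per group can detect, and for a gain from 27% that is .215 whichever effect was wanted.

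The intent-to-treat range is softer. It rests on an unknown split and on dropouts gaining nothing, and women with some sessions before stopping might be diluted less.

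**Conclusion.** The stated figure is wrong as written. With 105 per group at two-sided alpha .0167 and a control rate of 27%, the gain detectable with 80% power is .215 (to 48.5%, OR 2.55). Power for a gain of .172 is about .59, some 21 points below the stated .80. The conclusion holds under every test variant tried.

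The mismatch between adherent completers and the intent-to-treat analysis is a separate, secondary point. The plan's text establishes the mismatch. Its size, power of .67 to .80 for a true .215, depends on the assumptions stated with the calculation, and the main finding does not rest on it.

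**What to change.** In Sample Size and Power:

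1. Replace .172 with .215, and give both rates and the odds ratio together: 27.0% vs 48.5%, OR 2.55. Say that 27% is the assumed control rate and that the test is two-sided.
2. Add that power for a gain of .172 (27.0% vs 44.2%) is about .59.
3. Give power for the intent-to-treat set under a stated split of the 25% into loss to follow-up and intervention dropout, with the outcome assumed for dropouts, in place of power for adherent completers.

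This is a change of wording only, and enrolment stays at 280. The cost is a less favourable stated figure. If the sponsor in fact wants 80% power for a gain of .172, wording will not be enough: about 322 evaluable and 430 enrolled women would be needed before any allowance for dilution.

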The primary outcome variables of interest for the short-term efficacy of the AME intervention at 2 weeks postpartum (Aim 1) are 1) proportion of mothers providing 100% breast milk, 2) percentage of feedings that were breast milk, and 3) breastfeeding self-efficacy. Secondary breastfeeding outcomes for short-term efficacy include proportion of mothers with any breastfeeding, perceived milk supply, onset and days to lactogenesis II, and days to any formula and/or breastfeeding cessation. Secondary long-term efficacy outcomes (Aim 2), which will be assessed at all follow-up points until 12 months postpartum (or breastfeeding cessation/loss to follow-up), are duration of breastfeeding in days and any breastfeeding at postpartum follow-ups; the continuous and categorical type versions of breastfeeding exclusivity; and the proximal intervening outcomes (i.e., mediating variables) including the repeatedly measured breastfeeding self-efficacy and perceived milk supply.

Generalized linear mixed-effects modeling with linear contrasts will be used to examine the effect of treatment assignment (AME vs. attention control) for each repeatedly assessed outcome, with treatment group assignment as the between-subjects factor, time as the within-subjects factor, and an interaction between time and treatment group. Given the level of measurement and observed data distribution of the particular dependent variable, an appropriate error structure and link function to the linear predictors will be assumed. For example, for breastfeeding exclusivity and any breast feeding, each assessed as a binary variable, a binomial error structure will be assumed and a logit link to the predictors will be applied, while for the continuous type versions of breastfeeding exclusivity and the interval-scaled breastfeeding self-efficacy, a normal error

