distribution will be considered with an identity link to the linear predictors. Random effects for participants will also be included. Fixed and/or time-dependent covariates (e.g., pre-pregnancy BMI category [25.0-29.9; 3034.9; 35-39.9; 40+]) may be included secondarily to adjust for group imbalances or variables related to the dependent variables based on the literature or data screening results. Standard fit criteria (e.g., AIC and BIC) also will be used to identify the best-fitting repeated measures covariance structure. F-tests will test the main and interaction effects included in the model. Individual regression parameters will be estimated with confidence intervals. For each model, residual analyses will be conducted to identify sources of model misspecification, outliers, and influential observations. Sensitivity analyses will be performed to discern the impact of influential cases on modeling results. Linear contrasts will be specified in the repeated measures models to test whether the AME intervention demonstrates greater improvements in breastfeeding outcomes compared to the attention control at each time point, in particular, when conducting hypothesis testing on the primary short-term outcomes. Point and interval estimates will be obtained for each of the comparisons examined.

For event history type outcomes (e.g., breastfeeding duration, days to the onset of lactogenesis II, days to any formula) Cox proportional hazards regression methods will be applied to allow for possible censoring of the event of interest and inclusion of the fixed and time-dependent predictors. For summary outcomes (e.g., proportion of breast milk in-hospital), generalized linear modeling will be applied.

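### No multiplicity procedure is named for the three 2-week primary outcomes; the implied fixed .0167 is valid, but Holm at the same familywise .05 has equal or greater power (0 to about 9 points on exclusivity at OR 2.55)

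*Combined protocol and SAP*

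**What the plan says.** The Sample Size and Power section gives "testing of multiple hypotheses" as one reason for the enrolment target. It states .80 power for exclusivity at 2 weeks with 105 per group, "at an adjusted test-wise significance level of .0167". The detectable effect appears in two forms in that sentence: a difference in proportions of .172 and a "medium effect size of OR=2.55 using likelihood ratio chi-square statistics". The enrolment figure follows from the 210: "To ensure 210 participants with complete follow-up to 2 weeks and no protocol deviations, we will enroll 280 women".

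Analysis Strategies for Aims 1 and 2 lists the primary outcomes as "1) proportion of mothers providing 100% breast milk, 2) percentage of feedings that were breast milk, and 3) breastfeeding self-efficacy". The analysis is by intent to treat: "all participants will be included in analyses as randomized, regardless of protocol adherence/deviations, treatment received, or withdrawal". Linear contrasts from the repeated-measures models test each time point, "in particular, when conducting hypothesis testing on the primary short-term outcomes", and "Point and interval estimates will be obtained for each of the comparisons examined".

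The .0167 appears only in the power paragraph. Neither Bonferroni, Holm nor any other procedure is named, and no decision level is given beside the contrasts.

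**The concern.** Three primary outcomes and a test-wise level of .05/3 together imply that each outcome is judged against a fixed .0167. That controls familywise error but leaves power unused. Once one outcome has been declared at .0167, a closed procedure can test the remaining two at less strict levels with no loss of familywise control. The plan cites earlier effects on both continuous outcomes and powers the third, so it expects several outcomes to respond, which is the setting where a stepwise rule helps.

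There is also a practical gap. Suppose one outcome has p=.010 and a second has p=.020. The second is not significant under the fixed rule but is significant under Holm (.020 is below .025). The analysis section does not say which rule decides.

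**Working it through.** **Inputs from the plan.** Exclusivity rate .27 (taken as the control rate); OR 2.55 or difference .172; d=.45 for percentage of feeds and d=.53 for self-efficacy, both from earlier work; 105 per group complete and without deviations; 280 enrolled, so 140 per group if all are analysed.

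**Assumptions.** Two-sided tests; correlation of the three test statistics from 0 to .9 (the plan gives none); two-group tests in place of the mixed-model contrasts.

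**Step 1. Reproduce the plan's figure.** Control odds .27/.73 = .370; times 2.55 = .943; treated rate .943/1.943 = .485; difference .215. The likelihood ratio noncentrality is 2n[l(p1,p1) + l(p2,p2) - l(p1,m) - l(p2,m)], with l(x,y) = x ln y + (1-x) ln(1-y) and m the mean of the two rates. At n=105 it is 10.47, giving power .800 at .0167. The stated .80 reproduces under OR 2.55. Enrolment also reproduces: 210/.75 = 280.

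The stated difference of .172 does not match. From .27 it gives .442, OR (.442/.558)/(.27/.73) = 2.14 and power .587; .80 power would need about 161 per group.

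**Step 2. Power of each outcome at fixed .0167.** For the continuous outcomes the noncentrality is d√(n/2).

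| Outcome | 105 per group | 140 per group |
|---|---|---|
| Exclusivity, OR 2.55 | .800 | .910 |
| Percentage of feeds, d=.45 | .801 | .912 |
| Self-efficacy, d=.53 | .922 | .978 |

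**Step 3. Holm.** Order the p-values and compare them with .05/3, .05/2 and .05, stopping at the first failure. Power was simulated with 400,000 trivariate normal draws per setting, calibrated to Step 2 (or to the altered effects). Ranges run over the correlations.

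| Setting | Gain from Holm, in points |
|---|---|
| 105 per group; OR 2.55, d=.45, d=.53 | exclusivity and feeds 6-9 (.80 to .86-.89); self-efficacy about 0.5-4 |
| 140 per group, same effects | exclusivity and feeds 4-5 (.91 to .95-.96); self-efficacy about 0-1 |
| 140 per group, all effects diluted 25% (assumption) | exclusivity and feeds 8-11 |
| 105 per group; OR 2.55, both continuous effects halved | exclusivity 0-2.4; continuous outcomes about 7-11 |
| 105 per group; self-efficacy null | exclusivity and feeds 2-3 |
| 105 per group; only one outcome responds | about 0 on that outcome |
| 105 per group; exclusivity difference .172 | exclusivity 13-14 (.59 to .72-.73); feeds 4-7 |

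In the first setting the chance of declaring all three rises from .59-.75 to .78-.85. The chance of declaring at least one is identical under both rules in every setting, because Holm's first step is the Bonferroni test.

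**Step 4. Check on the approximation.** Participant-level simulation with percentage of feeds bounded at 100 and a point mass at 100% gave gains on exclusivity and feeds of 7-8 points at 105 per group and 4-5 at 140 (first-setting effects).

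**The case against.** The strongest reply is that the plan never commits to a fixed Bonferroni rule. The .0167 is a planning level, and someone intending Holm would size at the same figure because it is Holm's first step. This stands: Bonferroni is inferred from .05/3 and three outcomes. It changes the description of the gap rather than the remedy, since the analysis section must name the rule either way.

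Second, the favourable gains lean on d=.45 and d=.53. These come from earlier research that included normal weight women; they are not declared design effects for this trial, and the plan itself notes heterogeneity in published effects. This also stands, and it is why the low-gain settings belong beside the 6-9 points.

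Third, a fixed rule has a real merit: each test agrees with its Bonferroni interval, and the plan promises interval estimates. Preferring that agreement to a few points of power is defensible.

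A reader might infer that multiplicity is handled wrongly or that familywise error is inflated. It is not: .05/3 on each of three tests is valid under any dependence. A reader might also infer that the trial is underpowered at .0167. Under OR 2.55, exclusivity meets its .80 target at that level. Nor does the plan make success depend on all three outcomes, so the all-three figures describe the size of the effect and are not a design failure.

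**Conclusion.** This is an inexpensive improvement, not an error. The plan names no procedure, and its natural reading is valid but less powerful than Holm at the same familywise .05. Holm cannot declare fewer outcomes, whatever the effects or correlations. How many more it declares depends on how many effects are real. On exclusivity with OR 2.55 at 105 per group, the gain runs from about 0 to about 9 points, and the upper part of that range needs the continuous outcomes to respond about as strongly as in the earlier work.

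The 140-per-group figures assume complete 2-week data and, unless marked as diluted, full effects. All figures are two-group approximations to the planned contrasts. The base case is itself unsettled: .172 and OR 2.55 disagree at a .27 base, and the exclusivity gain (6-9 or 13-14 points at 105 per group) depends on which was meant.

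**What to change.** Before group results are seen, add beside the primary contrasts in Analysis Strategies for Aims 1 and 2:

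> The three 2-week primary contrasts are tested two-sided with the Holm step-down procedure at familywise alpha .05 (.0167, .025, .05). Holm-adjusted p-values decide significance. Bonferroni (98.33%) intervals are reported as conservative estimates and may include the null for an outcome that Holm declares significant.

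Keep .0167 as the planning level, and reconcile .172 with OR 2.55 in the power paragraph (OR 2.55 from .27 implies .215).

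The cost is a few sentences and no participants. There are two statistical downsides:

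- With OR 2.55, d=.45 and d=.53, the Holm test and the Bonferroni interval disagree for at least one outcome in about 11-20% of trials at 105 per group and 6-11% at 140.
- When the other two effects are real, the chance of wrongly declaring one null outcome rises from .017 to about .033-.045 at 105 per group and .034-.048 at 140. This stays within the .05 familywise limit.
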